5.2 Secondary Efficacy Endpoints

1. Scores on self-report Subjective Opiate Withdrawal Scale (SOWS)³ following administration of the test versus control products. A complete score that captures the full range of withdrawal responses may reveal a withdrawal syndrome that occurs, in addition to, or in the absence of, nausea.
2. Rate of the cortisol response following administration of the test versus control products as measured by salivary cortisol. Cortisol increases following opioidergic blockade may index the degree to which an individual's opioid system controls the hypothalamic-pituitary-adrenal (HPA) axis, which is responsible for physiologic stress responses.

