HIPAA	Health Insurance Portability and Accountability Act of 1996
ICF	Informed Consent Form
ICH	International Conference on Harmonisation
IEC	Independent Ethics Committee
IRB	Institutional Review Board
IM	Intramuscular
IN	Intranasal
IT	Information Technology
IUD	Intrauterine Device
IV	Intravenous
MAD	Mucosal Atomization Device
OS	Operating System
PI	Principal Investigator
SAE	Serious adverse experience
SID	Subject Identification Number
SC	Subcutaneous
SQL	Structured Query Language
SSL	Secure socket layer
UCSF	University of California – San Francisco
VPN	Virtual private network

PROTOCOL SYNOPSIS

TITLE	OPIATE WITHDRAWAL RESPONSES TO INTRANASAL NALOXONE AS AN INDEX OF ALTERED ENDOGENOUS OPIOID ACTIVITY AMONG WOMEN WITH OBESITY: A FEASIBILITY AND EFFICACY STUDY
SPONSOR	[name]
FUNDING ORGANIZATION	National Heart Blood and Lung Institute (NHLBI)
NUMBER OF SITES	1
RATIONALE	Understanding what drives compulsive overeating among individuals with obesity will lead to the development of more effective treatments. A large body of literature implicates the endogenous opioid system in eating behavior. Researchers have published the use of exogenous opioidergic blockade as a method to assess endogenous opioid activity in obesity ^{1,2} . Data suggest that women are more sensitive to exogenous opioidergic blockade. Our work shows that withdrawal responses, as indexed by nausea following opioidergic antagonism using oral naltrexone, are associated with non-homeostatic eating in obese women ^{1,2} . To (1) reduce the amount of time needed to investigate associations between eating behavior, obesity, and the endogenous opioid system, thereby reducing subject burden, and (2) take the initial steps toward the development of a cost-and time-effective method to assess endogenous opioid activity in women, we plan to evaluate the use of naloxone hydrochloride administered intranasally (intranasal naloxone).
STUDY DESIGN	This is a single-center, double-blind, placebo-controlled, randomized, crossover trial design.
PRIMARY OBJECTIVE	1. To determine if 2 mg/2 mL intranasal naloxone elicits the withdrawal symptom of nausea (present versus absent) in obese women.
SECONDARY OBJECTIVES	1. To determine if 2 mg/2 mL intranasal naloxone elicits other withdrawal symptoms, as measured by subjective opiate withdrawal scales ³ in obese women 2. To determine the rate of the cortisol response following 2 mg/2 mL intranasal naloxone in obese women
NUMBER OF SUBJECTS	24 women

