DURATION OF SUBJECT PARTICIPATION AND DURATION OF STUDY	Subjects will be in the study for up to 3 weeks. There will be a period of at least 24 hours between visits 1 and 2. Web-based eligibility: Screening for self-report eligibility criteria, approx. 15 minutes Phone Screen: Phone call to review eligibility and schedule visit 1, planning for visit 1, approx. 15 minutes Visit 1: In-person baseline assessment (screening for pregnancy and

	drug use), approx. & Administration day 1 (approximately 1.5-2 hours) Visit 2: Administration day 2 (approximately 1.5-2 hours) Recruitment and participation are expected to take 6 months
CONCOMITANT MEDICATIONS	
Allowed:
 
 1. Medications are permitted with use of naloxone hydrochloride unless listed below under “prohibited” 
Prohibited:
 
 1. Current use of opiate-containing medications 2. Current use of vasoconstrictor medication 3. Initiation of new medications that are contraindicated with naloxone hydrochloride use during the study period 4. Current use of insulin
EFFICACY EVALUATIONS	
 1. Self-reported nausea at 0 minutes (pre-administration), and 10 and 30 minutes following administration of test product or control product 2. Self-reported symptoms of withdrawal as measured by the subjective opiate withdrawal scale (SOWS³) at 0 minutes (pre-administration), and 10 and 30 minutes following administration of test product or control product 3. Salivary cortisol values at 0 minutes (pre-administration) and 20 and 50 minutes following administration of test product or control product
PRIMARY ENDPOINT	
 1. Presence or absence of the self-reported withdrawal symptom of nausea following administration of the test versus control product.
SECONDARY ENDPOINTS	
 1. Scores on self-report Subjective Opiate Withdrawal Scale (SOWS)³ following administration of the test versus control product. 2. Rate of the cortisol response, as measured by salivary cortisol, following administration of the test versus control product.
OTHER EVALUATIONS	N/A
SAFETY EVALUATIONS	Incidence of unexpected adverse events. Subjects will be monitored for unexpected adverse events and serious adverse events following administration of the test product and control product.

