3 STUDY OBJECTIVES

3.1 Primary Objective

1. To determine if 2 mg/2 mL intranasal naloxone (1 mg/1 mL per nostril) elicits the withdrawal symptom of nausea (present versus absent) in obese women (compared to intranasal placebo).

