3.2 Secondary Objectives

1. To determine if 2 mg/2 mL intranasal naloxone (1 mg/1 mL per nostril) elicits other withdrawal symptoms, as measured by subjective opiate withdrawal scales³ in obese women (compared to intranasal placebo).
2. To determine the rate of the salivary cortisol response following intranasal naloxone administration in obese women (compared to intranasal placebo).

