- Randomization: [name] will report the subject's ID number and eligibility status to the unblinded study staff, who will consult the randomization table generated by the UCSF Research Pharmacy staff (which will dictate the ordering in which the subject will receive the test and control products at each visit).
- Taste Test Procedure: At visits 1 and 2, subjects will eat for 10 minutes from a food buffet that includes foods that they selected during visit 1 (different foods will be provided at each visits 1 and 2 so as not to repeat foods). All foods will be served in

large bowls and in large quantities, factors that are known to non-consciously increase intake⁴⁰. Bowls of food will be weighed before and after the “taste test” period and this information will be documented ([Appendix H](#)). As commonly done in studies involving hedonic eating, subjects will indicate (on paper forms) how much they liked each food on paper questionnaires after tasting each food, as done in prior studies examining the role of opioid involvement in liking of foods^{41,42}.

- *Administration of Test Product (Intranasal Naloxone) or Control Product (Intranasal Placebo)*: Subjects will receive each the test product (intranasal naloxone) (2 mg/ 2 mL, 1 mg/1 mL per nostril) and control product (intranasal placebo, 1 mL per nostril) via a nasal mucosal atomization device (MAD; [See 8.4.3 Syringe Assembly](#)) in a randomized order (per the randomization table generated by the UCSF Research Pharmacy and accessible only to unblinded study staff) on visits 1 and 2, immediately following the food buffet procedure.
- *Self-Report Measures*: Subjects will self-report their level of nausea (present versus absent) in the context of completing the SOWS³ prior to receiving either the test or control product, as well as 10 and 30 minutes after receiving the test or control product.
- *Saliva Samples (Salivary Cortisol)*: Subjects will provide saliva samples prior to receiving the test and control products, as well as 20 and 50 minutes after receiving the test or control products.

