22 APPENDIX E: SCHEDULE OF EVENTS BY STUDY VISIT

Protocol Institutional Review Board #: _____

Protocol Title: Opiate withdrawal responses to intranasal naloxone as an index of altered endogenous opioid activity among individuals with obesity: A feasibility and efficacy study

Principal Investigator: [name] PhD

Sponsor: [name]

	VISIT 1	VISIT 2 ^a
Informed Consent	X	
Medical History	X	
Height	X	
Weight	X	
Demographics	X	
Pregnancy Test (Urine)	X	
Drug Screen (Urine)	X	
Measures of Eating Behavior (Self-Report)	X	
Randomization	X	
Food Buffet Menu Selection	X	
Vital Signs (Pulse Rate, Temperature, Blood Pressure)	X	
Taste Test Procedure	X	X
Administration of Control Product or Test Product	X	X
Self-report Measures of Nausea (SOWS)	X	X
Saliva	X	X
Adverse Experiences	X	X
Concomitant Medication Review	X	X

^a At least 24 hours after Visit 1

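### Secondary objective 1 asks about withdrawal symptoms other than nausea, but its endpoint is a complete SOWS score that very probably includes nausea

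*Combined protocol and SAP*

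**What the plan says.** - **Primary objective (3.1).** To determine whether intranasal naloxone "elicits the withdrawal symptom of nausea (present versus absent) in obese women (compared to intranasal placebo").
- **Secondary objective 1 (3.2, and the same in the Synopsis).** Whether naloxone "elicits other withdrawal symptoms, as measured by subjective opiate withdrawal scales".
- **Endpoint for that objective (5.2).** SOWS scores after test versus control product, with this rationale: "A complete score that captures the full range of withdrawal responses may reveal a withdrawal syndrome that occurs". The sentence goes on to say that the score "may reveal a withdrawal syndrome that occurs, in addition to, or in the absence of, nausea".
- **How nausea is collected (section 10, Self-Report Measures).** "Subjects will self-report their level of nausea (present versus absent) in the context of completing the" SOWS, before administration and 10 and 30 minutes after it.
- **Schedule of events (Appendix E).** The only row that mentions the SOWS reads "Self-report Measures of Nausea (SOWS").
- **Synopsis, Efficacy Evaluations.** Nausea has its own entry ("Self-reported nausea at 0 minutes (pre-administration), and 10 and 30 minutes following administration"), and the SOWS has a second entry at the same three times.
- **Analysis (15.4).** Only the cortisol model is described. There is no SOWS scoring rule, item handling or model.

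**The concern.** Secondary objective 1 is meant to add something to the primary objective, namely whether naloxone produces withdrawal symptoms beyond nausea. A total that contains the nausea item cannot show this by itself. If naloxone causes nausea and nothing else, the total still rises, and the result can be read as support for objective 1 although it only repeats the primary finding.

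Section 5.2 says that the score may reveal a syndrome in addition to nausea or without it, so the sponsor wants to tell these apart. No score or rule in the plan does that. The study is meant to supply preliminary data for later treatment-matching work (section 2), so whether the response is nausea alone or a wider syndrome is one of its more useful outputs.

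**Working it through.** The plan states no figure for the SOWS endpoint, so there is none to reproduce. The check has a textual part and an illustrative part.

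**1. The text, step by step**

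1. In 3.2 the word for other symptoms can only mean other than nausea, because 3.1 has taken nausea as its own question.
2. The endpoint in 5.2 is a complete score over the full range of responses, with nothing left out.
3. Section 10 takes the nausea report while the SOWS is being completed, and Appendix E labels the SOWS row as the nausea measure. The two Synopsis entries share the times 0, 10 and 30 minutes. Together these make nausea very probably a SOWS item.
4. That the item is summed into the score is not stated anywhere. It is inferred from the description of the score as complete.
5. No section defines a score without nausea, and 15.4 does nothing later to separate it.

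**2. How large could the effect be?**

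Inputs from the documents: N = 24, crossover (4.1), and the six pairs of nausea rates in the power table of 15.5 (control vs test: 0 vs 20%, 0 vs 30%, 0 vs 40%, 10 vs 40%, 20 vs 50%, 30 vs 60%).

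Assumptions, none of them in the documents:
- paired t-test, two-sided .05;
- nausea adds w = 1 or 2 points to the score;
- no effect on the other items, whose paired difference is Normal with mean 0 and SD s = 1, 2, 3 or 5;
- nausea independent between visits.

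For each subject the paired difference has

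mean = w × (p1 − p0), variance = s² + w² × [p1(1 − p1) + p0(1 − p0)],

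so the noncentrality is √24 × mean / √variance.

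*Largest case* (w = 2, s = 1, 0 vs 40%): mean = 2 × 0.40 = 0.80; variance = 1 + 4 × 0.24 = 1.96; noncentrality = 4.899 × 0.80 / 1.40 = 2.80. The noncentral t gives .765, and simulation gives .771.

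*Smallest case* (w = 1, s = 5, 0 vs 20%): mean = 0.20; variance = 25 + 0.16 = 25.16; noncentrality = 4.899 × 0.20 / 5.016 = 0.195. The noncentral t gives .054, and simulation gives .052.

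The table gives the chance that a nausea-only effect makes the complete score significant (40,000 simulated trials per cell):

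| Control vs test | w | s = 1 | s = 2 | s = 3 | s = 5 |
|---|---|---|---|---|---|
| 0 vs 20% | 1 | .136 | .075 | .061 | .052 |
| 0 vs 30% | 1 | .245 | .102 | .073 | .060 |
| 0 vs 40% | 1 | .392 | .147 | .094 | .067 |
| 10 vs 40% | 1 | .234 | .103 | .077 | .060 |
| 20 vs 50% | 1 | .219 | .104 | .074 | .058 |
| 30 vs 60% | 1 | .217 | .103 | .075 | .058 |
| 0 vs 20% | 2 | .296 | .133 | .092 | .065 |
| 0 vs 30% | 2 | .541 | .247 | .144 | .086 |
| 0 vs 40% | 2 | .771 | .388 | .223 | .114 |
| 10 vs 40% | 2 | .455 | .233 | .139 | .088 |
| 20 vs 50% | 2 | .409 | .219 | .141 | .084 |
| 30 vs 60% | 2 | .394 | .219 | .143 | .087 |
| Nausea item removed | – | .050 | .052 | .050 | .049 |

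Of the 48 cells, 31 are .15 or lower, and the median is .12.

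**3. Sensitivity to the assumed score distribution**

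- *Zero-heavy scores.* Other-item score 0 at 70% of readings and 1 to 4 otherwise: .08 to .17 with w = 1, .15 to .44 with w = 2, and about .05 with no nausea contribution.
- *Item-level simulation* (20,000 trials per scenario). 10 or 16 items, scored 0/1 or 0 to 3, other items endorsed at 2%, 5% or 10% in both conditions. With nausea at 20% vs 0%, the complete score is significant in about 8% to 26% of trials. At 40% vs 0%, it is about 17% to 70%. With the nausea item removed, it is about 4% to 5% throughout.

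**The case against.** **The key premise is not in the text.** No section lists SOWS items or scoring, and the Synopsis lists nausea and the SOWS as two evaluations. A yes/no nausea question asked next to the SOWS would also fit section 10. Even the instrument's name is unsettled: 5.2 calls it the subjective scale, while the cited reference describes a short scale. This stands as a limit on certainty. It does not remove the point, because one sentence in 5.2 would resolve it and the plan lacks that sentence.

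**The complete score may be deliberate.** Section 3.2 names the scale as its measure and 5.2 gives a reason for the full range. On that reading, nausea belongs in a withdrawal score and a nausea-driven rise is a real effect on the stated endpoint. This is a fair defence of reporting the complete score, and the fix keeps it. It does not make that score an answer to the question in 3.2. Deleting the word for other from 3.2 and the Synopsis would remove the mismatch, but only by changing the question.

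**The figures carry little weight.** Item weight, SD, independence and test are all assumed, and three of the six rate pairs have nausea on control although 15.5 expects none. This is accepted. The figures show only that the effect can be anything from negligible to large.

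**The consequence is limited.** This is one secondary endpoint in a 24-subject feasibility study, and a reader can set the nausea and SOWS results side by side. That is true and keeps the point modest. Without a rule fixed in advance, however, the comparison is made after the data are seen. A nausea-free score also does not by itself separate a syndrome with nausea from one without it. That needs the score set against each subject's nausea status.

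**Conclusion.** The concern holds. The objective asks about symptoms other than nausea, the endpoint is a complete score, and the documents place the nausea report within that instrument. No score without nausea is defined, so a nausea-only effect can count toward secondary objective 1.

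The conclusion rests on one inference, that nausea is summed into the score. This is very probable but not stated. The size cannot be estimated from the documents. Under the assumptions shown, the chance of a significant complete score from nausea alone runs from .05 to .77, is .15 or lower in most scenarios, and returns to about .05 once the item is removed. This is a worthwhile, inexpensive improvement to a secondary endpoint. It does not affect the primary analysis.

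**What to change.** - **In 5.2:** state whether nausea is a scored SOWS item. If it is, assess objective 1 with the SOWS score excluding that item, and report the complete score alongside it. If it is not, one sentence saying so resolves the overlap.
- **In 15.4:** name a within-subject comparison of that score between conditions, using the 0-minute value already collected at each visit. This also fills a separate gap, since 15.4 has no SOWS analysis at present.
- **Instrument:** reconcile the scale's name in 5.2 with the cited reference, because the item list depends on it.

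The cost is wording only. The SOWS is already completed at 0, 10 and 30 minutes at both visits, so no data, visits or subjects are added. The one drawback is that the nausea-free score is not the published total, which is why the complete score stays in the report.

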5.3 Safety Evaluations

Incidence of unexpected adverse events.

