9.1.6 Adverse Events

Information regarding occurrence of adverse events will be captured throughout the study. Duration (start and stop dates), severity, outcome, treatment and relation to study drug will be recorded on case report forms (CRFs).

92 Clinical Laboratory Measurements

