11 ADVERSE EXPERIENCE REPORTING AND DOCUMENTATION

11.1 Adverse Events

An adverse event (AE) is any untoward medical occurrence in a clinical investigation of a subject administered a pharmaceutical product and that does not necessarily have a causal relationship with the treatment. An AE is therefore any unfavorable and unintended sign (including an abnormal laboratory finding), symptom or disease temporally associated with the administration of an investigational product, whether or not related to that investigational product. An unexpected AE is one of a type not identified in nature, severity, or frequency in the current Investigator’s Brochure or of greater severity or frequency than expected based on the information in the Investigator’s Brochure.

The Investigator will probe, via discussion with the subject, for the occurrence of AEs during each subject visit and record the information in the Adverse Event Accountability Log ([Appendix I](#)) and in the subject’s CRF. Adverse events will be described by duration (start and stop dates and times), severity, outcome, treatment and relation to study drug, or if unrelated, the cause.

AE Severity

The guidelines shown in Table below should be used to grade severity. It should be pointed out that the term “severe” is a measure of intensity and that a severe AE is not necessarily serious.

Table 3. AE Severity Grading

Severity (Toxicity Grade)	Description
Mild (1)	Transient or mild discomfort; no limitation in activity; no medical intervention or therapy required. The subject may be aware of the sign or symptom but tolerates it reasonably well.
Moderate (2)	Mild to moderate limitation in activity, no or minimal medical intervention/therapy required.
Severe (3)	Marked limitation in activity, medical intervention/therapy required, hospitalizations possible.
Life-threatening (4)	The subject is at risk of death due to the adverse experience as it occurred. This does not refer to an experience that hypothetically might have caused death if it were more severe.

AE Relationship to Study Drug

The relationship of an AE to the study agent should be assessed using the following the guidelines in Table .

Table 4. AE Relationship to Study Drug

Relationship to Drug	Comment

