11.2.1 Serious Adverse Experience Reporting

All SAEs that occur (whether or not related to study drug) will be documented per UCSF CHR (IRB) Guidelines

(http://www.research.ucsf.edu/chr/guide/Violation_Incident_Guidelines.asp). The collection period for all SAEs will begin after informed consent is obtained and end after procedures for the final study visit (visit 2) have been completed.

In accordance with the standard operating procedures and policies of the local Institutional Review Board (IRB)/Independent Ethics Committee (IEC), the site investigator will report SAEs to the IRB/IEC.

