The safety and effectiveness of naloxone hydrochloride in patients with liver disease have not been established in well-controlled clinical trials. Caution should be exercised when naloxone hydrochloride is administered to patients with liver disease.

ADVERSE REACTIONS**Postoperative**

The following adverse events have been associated with the use of naloxone hydrochloride in postoperative patients: hypotension, hypertension, ventricular tachycardia and fibrillation, dyspnea, pulmonary edema, and cardiac arrest. Death, coma, and encephalopathy have been reported as sequelae of these events. Excessive doses of naloxone hydrochloride in postoperative patients may result in significant reversal of analgesia and may cause agitation (see **PRECAUTIONS** and **DOSAGE AND ADMINISTRATION; Usage in Adults-Postoperative Opioid Depression**).

Opioid Depression

Abrupt reversal of opioid depression may result in nausea, vomiting, sweating, tachycardia, increased blood pressure, tremulousness, seizures, ventricular tachycardia and fibrillation, pulmonary edema, and cardiac arrest which may result in death (see **PRECAUTIONS**).

Opioid Dependence

Abrupt reversal of opioid effects in persons who are physically dependent on opioids may precipitate an acute withdrawal syndrome which may include, but is not limited to, the following signs and symptoms: body aches, fever, sweating, runny nose, sneezing, pilo-erection, yawning, weakness, shivering or trembling, nervousness, restlessness or irritability, diarrhea, nausea or vomiting, abdominal cramps, increased blood pressure, tachycardia. In the neonate, opioid withdrawal may also include: convulsions; excessive crying; hyperactive reflexes (see **WARNINGS**).

Adverse events associated with the postoperative use of naloxone hydrochloride are listed by organ system and in decreasing order of frequency as follows:

Cardiac Disorders: pulmonary edema, cardiac arrest or failure, tachycardia, ventricular fibrillation, and ventricular tachycardia. Death, coma, and encephalopathy have been reported as sequelae of these events.

Gastrointestinal Disorders: vomiting, nausea

Nervous System Disorders: convulsions, paraesthesia, grand mal convolution

Psychiatric Disorders: agitation, hallucination, tremulousness

Respiratory, Thoracic and Mediastinal Disorders: dyspnea, respiratory depression, hypoxia

Skin and Subcutaneous Tissue Disorders: nonspecific injection site reactions, sweating

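### The safety endpoint counts only unexpected adverse events and no summary by product is planned, so expected, non-serious reactions are recorded but left out of the defined safety result

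*Combined protocol and SAP*

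**What the plan says.** Section 5.3 consists of one line: "Incidence of unexpected adverse events". The synopsis repeats it and adds: "Subjects will be monitored for unexpected adverse events and serious adverse events following administration of the test product and control product".

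Section 11.1 defines the key word in two limbs, both tied to an Investigator's Brochure: "An unexpected AE is one of a type not identified in nature, severity, or frequency in the current" brochure, "or of greater severity or frequency than expected based on the information in the" same document.

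Collection is wider than the endpoint. Section 9.1.6 states: "Information regarding occurrence of adverse events will be captured throughout the study". Section 11.1 states: "The Investigator will probe, via discussion with the subject, for the occurrence of AEs during each subject visit and record the information" in the AE log and the case report form, with severity and relation to study drug. Section 11.2.1 states: "All SAEs that occur (whether or not related to study drug) will be documented".

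Section 15 covers the analysis set, baseline characteristics, McNemar's test for nausea, a mixed model for cortisol, and sample size. It contains no safety analysis.

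**The concern.** An endpoint limited to unexpected events answers whether anything surprising happened. It does not answer how often subjects had adverse effects on naloxone compared with saline. The title describes a feasibility and efficacy study, and sections 2 and 2.1 present the method as a low-burden, non-invasive test for later use in women with obesity. The second question bears on that aim.

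The crossover is well suited to answer it, because each subject receives both products and is her own control. As written, the plan collects the information and then defines a safety result that does not use all of it. What reaches the report beyond unexpected events would be decided after the data are seen.

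The definition also depends on a classification that the documents do not pin down, so two careful readers could count the same event differently.

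**Working it through.** The plan states no figure for safety, so there is nothing to reproduce. The check sets the relevant sections side by side.

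**Step 1. Endpoint against collection and analysis.**

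| Item | Where | Scope |
|---|---|---|
| Safety endpoint | 5.3, synopsis | Unexpected AEs only |
| AE collection | 9.1.6, 11.1 | All AEs, with severity (Table 3) and relatedness (Table 4) |
| Serious AEs | Synopsis, 11.2.1 | Monitored; all documented, related or not |
| AE analysis by product | 15 | None |

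The class left out is therefore non-serious AEs that are not unexpected. They are in the database but in no defined result.

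**Step 2. What is not unexpected.** Under section 11.1 an event escapes the endpoint only if it fails both limbs: its type is already identified in the reference document, and it is neither more severe nor more frequent than that document leads one to expect.

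**Step 3. Which reference document.** Section 11.1 names an Investigator's Brochure. The product reference appended, and drawn on in sections 1.1 and 1.2, is the package insert in Appendix A. Take one non-serious vomiting episode and use the insert as the reference:

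- *Read as expected.* The insert lists "Gastrointestinal Disorders: vomiting, nausea".
- *Read as unexpected.* That entry concerns postoperative use. Vomiting appears elsewhere in the insert in connection with opioid reversal, opioid dependence or septic shock. The subjects here are excluded for opiate use in the last 30 days (section 6.3), and the insert describes naloxone at usual doses without opioids as having essentially no pharmacologic activity. Its report on normal subjects, at 2 mg/kg, mentions nausea, sweating, dizziness and stomachaches but not vomiting.

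The frequency part of the second limb does not settle the matter. The insert ranks postoperative reactions in decreasing order of frequency but gives no rates, so it offers no benchmark for a frequency greater than expected.

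**Step 4. How many events could be affected.** This is an illustration on assumed rates; the documents give none. Let p be the probability that a subject vomits after naloxone, independently across the 24 subjects planned.

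- Expected cases = 24 × p
- Chance of at least one = 1 − (1 − p)^24

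| Assumed p | Expected cases | Chance of at least one |
|---|---|---|
| 5% | 24 × 0.05 = 1.2 | 1 − 0.95^24 = 71% |
| 10% | 24 × 0.10 = 2.4 | 1 − 0.90^24 = 92% |
| 15% | 24 × 0.15 = 3.6 | 1 − 0.85^24 = 98% |

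Across this range at least one case is more likely than not. Whether those cases enter the safety result depends on the unsettled classification in step 3.

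**The case against.** The strongest reply is that little is missing. All AEs are probed for and logged, so a table by product could be made at any time. The drug is given in order to elicit withdrawal symptoms: nausea is the primary endpoint, compared between products by McNemar's test, and the withdrawal scale is a secondary endpoint collected at both visits. It is then natural for safety to look at what is not expected. This stands in part. Nausea is indeed analysed, and the gap is not in data capture. But section 15.4 describes an analysis for cortisol only and none for the withdrawal scale, and neither efficacy measure carries the severity and relatedness grading used for AEs.

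A reader might go further than the documents allow, in four ways:

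- *All known naloxone reactions are excluded.* They are not. The second limb in section 11.1 brings back any that are more severe or more frequent than expected, and serious events, such as a serious seizure, are monitored and documented whether or not they are expected.
- *Several subjects could vomit and the plan would necessarily report zero.* This is not established. In opioid-free women such events could be classed as unexpected and so counted.
- *Blood-pressure changes are lost through the endpoint wording.* This is a poor example. Section 9.1.5 and Appendix E place blood pressure at visit 1, section 10 lists it under both visits, and none specifies a reading after administration. Rewording the endpoint would not capture such changes systematically; that is a separate matter.
- *The study claims that the test is tolerable.* The documents do not say so. They speak of cost, time, subject burden and being non-invasive.

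**Conclusion.** The point holds in a limited form. The defined safety result omits expected, non-serious reactions of ordinary severity and frequency, and no AE summary by product is planned, although the data for one are collected. The reference for expectedness is not settled between the brochure that section 11.1 names and the insert that the protocol supplies, so the same event could be classed either way.

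This is a fault of endpoint definition and reporting. It does not affect the primary nausea analysis or the documentation of serious events. Its size cannot be fixed from the documents: the vomiting figures rest on assumed rates of 5% to 15% and on independence between subjects, and they give the number of events whose classification would matter, not the number certain to be lost. The change is worth making because it is cheap and removes a choice that would otherwise be made after the data are seen.

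**What to change.** 1. In section 5.3 and the synopsis, define the safety endpoint as the incidence of all AEs and serious AEs by product received (naloxone or placebo), by severity and relatedness, with unexpected AEs reported as a subset.
2. In section 15, add one descriptive table of AEs by product. Without this step the wider endpoint would still have no planned analysis.
3. In section 11.1, name the document against which expectedness is judged. If it is the Appendix A insert, say how its postoperative and opioid-related entries apply to opioid-free subjects.

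The cost is a few wording changes and one extra table. No new data are needed: severity and relatedness are already recorded, and after unblinding each event can be assigned to a product from the subject number and dates in the AE log (Appendix I) and the product accountability log (Appendix D).
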